8.12 Treatment Accountability and Compliance

The pharmacist or other designated individual will maintain records of study treatment delivered to the study site; the inventory at the site; the distribution to and use by each patient; and the return of materials to the sponsor or disposal. These records should include dates, quantities, batch/serial numbers, expiration dates, in-clinic temperature log, and unique code numbers assigned to the product and study patients.

Patients will receive MOR00208 under the direct supervision of study personnel. Each administration volume or dose will be checked and the vial/outer package code and volume or dose per administration will be recorded in each patient's eCRF as well as in the source data.

At each visit after initiation of treatment, site staff will record compliance of patients with their assigned regimen. Patients will be instructed to bring unused/partially used/empty medication containers of idelalisib or venetoclax back for inspection on Day 1 of each cycle, starting with Cycle 2, or on the EOT visit as compliance will be assessed by tablet counts.

Patients are to be reminded of the importance of compliance with their assigned regimen, with an emphasis on taking their study drug on schedule, and maintaining the prescribed interval between doses.

Investigators will maintain records that document adequately that the patients were provided with the correct study treatment kits and will reconcile the products received from the drug dispensing center. Drug accountability will be checked by the field monitor during site visits and at the completion of the trial.

Noncompliance in general is defined as taking $\leq 80\%$ or $>120\%$ of one MOR00208 dose and/or $\leq 80\%$ or $>120\%$ of the idelalisib or venetoclax intake per cycle during any outpatient evaluation period.

Moreover, one MOR00208 dose can be missed between Cycles 1 and 3, between Cycles 4 and

12 and one dose between Cycles 13 and 24 without the patient being non-compliant. Note that MOR00208 dose omissions due to toxicity are covered in Sections 8.6 and 8.9.

Discontinuation for noncompliance is at the Investigator's discretion and is to be noted on the eCRF.

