4.7.1.3 Exposure Analysis

- The number of patients completing each cycle will be summarized and listed. A patient is considered to have completed a cycle for MOR00208 if he/she was compliant for all MOR00208 infusions during the cycle. A patient is considered to have completed a cycle for idelalisib or venetoclax if he/she was compliant for idelalisib or venetoclax administration during the cycle.
- Duration of exposure will be calculated for the following categories: Week (1-2], (2-4], (4-6], (6-8], etc. Summaries (i.e., mean, standard deviation, etc.) will be displayed in weeks.
- Number of infusions with MOR00208 will be summarized.

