4.7.4 Treatment Compliance

If the ratio (total used dose)/(total planned dose) is between 80% (exclusive) and 120% (inclusive) of the assigned dosage during a particular Cycle, then the patient is considered compliant for treatment.

The planned dose and the used dose will be calculated based on information collected on the eCRF pages '*Idelalisib Dosing Record*' or '*Venetoclax Dosing Record*'. As patients may change the daily dose, or transiently interrupt treatment, information on dosing will be represented differently in the eCRF for different situations:

- Patients who changed the Actual Total Daily Dose have **two (or more)** eCRF log lines for a particular Cycle or treatment period (during venetoclax ramp-up), i.e., one separate log line for each particular Actual Total Daily Dose. Each eCRF log line will contain information on the number of tablets dispensed, and the number of tablets returned.
- Patients who interrupted treatment and re-initiated treatment in the same_Cycle (or same treatment phase during ramp-up) have **two (or more)** eCRF log lines. The Actual Total Daily Dose in each log line will be identical. All eCRF log lines will contain the information on the number of tablets dispensed, and the last log line will contain the information on the number of tablets returned.
- Patients who interrupted treatment, and only re-initiated treatment at the beginning of the next Cycle or next treatment period (during venetoclax ramp-up) will have **one** eCRF log line containing all information on Actual Total Daily Dose, number of tablets dispensed, and number of tablets returned.
- Compliant patients will display only one eCRF log line for a particular cycle, or treatment phase.

The number of days on treatment for a particular Actual Total Daily Dose (represented by an individual eCRF log line) is calculated as follows:

$(\text{Dosing Stop Date} - \text{Dosing Start Date}) + 1$.

The number of days on treatment will be derived for every single eCRF log line.

Idelalisib

Idelalisib is dispensed in 28-day Cycles. The administration is bi-daily (100 mg BID or 150 mg BID). Compliance will be calculated based on the total planned dose, and the total dose actually used.

- The total ***planned*** dose per Cycle can be calculated as follows:
 - **For Cycles with one eCRF log line:**
Actual Total Daily Dose as entered in the eCRF [mg] x Number of days on treatment.

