 - **For patients and Cycles with two or more eCRF log lines:**
 - ❖ **All log lines contain information on the number of tablets dispensed, and number of tablets returned (in case of dose change):**
[(Actual Total Daily Dose as entered in the eCRF [mg] in log line 1 / Factor X) x (Number of tablets dispensed in log line 1 – Number of tablets returned in log line 1)] + [(Actual Total Daily Dose as entered in the eCRF [mg] in log line 2 / Factor X) x (Number of tablets dispensed in log line 2 – Number of tablets returned in log line 2)].
 - ❖ **All log lines for a particular Cycle contain the information on the number of tablets dispensed, and only the last log line for a particular Cycle contains the information on number of tablets returned (in case of treatment interruption and re-initiation of treatment in the same Cycle):**
[(Actual Total Daily Dose as entered in the eCRF [mg] in log line 1 / Factor X) x (Number of tablets dispensed in log line 1) - [(Actual Total Daily Dose as entered in the eCRF [mg] in log line 2 / Factor X) x (Number of tablets returned in log line 2)].
- Calculation of compliance for a particular Cycle (%):
(sum of total dose ***used*** for all log lines pertaining to a particular Cycle) / (sum of total ***planned*** dose for all log lines pertaining to a particular Cycle) * 100.

MOR00208

A patient will be considered compliant with the protocol if the MOR00208 dose administered is >80% and ≤120% of the planned dosage per single infusion. Therefore MOR00208 compliance will be presented for each infusion.

Furthermore, MOR00208 dosage will be summarized by cycle as well. The total administered dose per cycle will be divided by the total planned dose per cycle. One MOR00208 dose can be missed between Cycles 1-3, between Cycles 4-12 and one dose between Cycles 13-24 without the patient being non-compliant (skipped doses of MOR00208 due to toxicity will not be considered for calculation of compliance).

A summary displaying the number and percentage of patients in the following categories will also be presented for each study drug, and each cycle:

- ≤80%
- >80 – 120%
- >120%

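### SAP 4.7.4 sets conflicting compliance rules for MOR00208, and leaves open whether infusions skipped for toxicity count in the dose denominator

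*SAP*

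**What the plan says.** SAP 4.7.4 opens with a general rule: a patient whose ratio of used to planned dose "is between 80% (exclusive) and 120% (inclusive) of the assigned dosage during a particular Cycle, then the patient is considered compliant for treatment". For MOR00208 it then adds four statements.

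1. Per infusion, a patient is "considered compliant with the protocol if the MOR00208 dose administered is >80% and ≤120% of the planned dosage per single infusion".
2. Per cycle, "The total administered dose per cycle will be divided by the total planned dose per cycle". Formulas for the planned dose are given for idelalisib and venetoclax, but none for MOR00208.
3. An allowance: "One MOR00208 dose can be missed between Cycles 1-3, between Cycles 4-12 and one dose between Cycles 13-24 without the patient being non-compliant".
4. In parentheses after the allowance: "skipped doses of MOR00208 due to toxicity will not be considered for calculation of compliance".

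The section ends with a table of patients per drug and per cycle in three classes: up to and including 80%, above 80% to 120%, and above 120%.

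SAP 4.7.1.3 carries compliance into the exposure analysis: "A patient is considered to have completed a cycle for MOR00208 if he/she was compliant for all MOR00208 infusions during the cycle".

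The allowance comes from Protocol 8.12 ("one MOR00208 dose can be missed between Cycles 1 and 3", and likewise for the two later windows), which also says: "Note that MOR00208 dose omissions due to toxicity are covered in Sections 8.6 and 8.9".

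**The concern.** A missed infusion can be compliant under one sentence of SAP 4.7.4 and non-compliant under the others, and the SAP states no order of precedence. Two programmers working from the same text could report different numbers of compliant patients and completed cycles. With about 12 patients per cohort, each patient classified differently moves a percentage by 1/12 = 8.3 points.

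The toxicity exclusion matters for a separate reason. MOR00208 doses may not be reduced (Protocol 8.6; SAP 4.7.2), so toxicity acts on its delivery through infusions withheld, omitted or stopped. The primary objective is the safety of the combination. A reader will therefore want to know what share of the scheduled antibody was given, and Tables 14.3.7.5.1 and 14.3.7.5.2 present exposure and compliance under one title.

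**Working it through.** **Inputs.** The schedule in SAP 3.3.2 gives 5 infusions in Cycle 1 (four weekly plus the Day 4 loading dose), 4 in each of Cycles 2 and 3, 2 in each of Cycles 4 to 6, and 1 per cycle from Cycle 7. The compliance limits are those of SAP 4.7.4. All infusions are assumed to be of equal dose. The plan states no figure of its own to reproduce.

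**Step 1: one missed dose, ratio by cycle.** Ratio = (planned - 1) / planned.

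| Cycle | Planned | Ratio after one miss | Class |
|---|---|---|---|
| 1 | 5 | 4/5 = 80% | 80% or less |
| 2-3 | 4 | 3/4 = 75% | 80% or less |
| 4-6 | 2 | 1/2 = 50% | 80% or less |
| 7 onwards | 1 | 0/1 = 0% | 80% or less |

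Each cycle fails the general per-cycle rule and lands in the lowest class. The missed infusion is itself 0% of its planned dose, so it also fails the per-infusion rule. The allowance nevertheless says that the patient is not non-compliant.

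Two limits apply. Cycle 1 sits exactly on the bound: if the other four infusions average d% of plan, the ratio is 4d/5, which exceeds 80% as soon as d exceeds 100. From Cycle 7, Protocol 8.6 directs that a dose missed for toxicity in monthly treatment be given after resolution, so 0% arises only if no made-up dose falls within that cycle.

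**Step 2: the same miss over the allowance window.**

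- Cycles 1-3: 5 + 4 + 4 = 13 planned; 12/13 = 92.3%.
- Cycles 4-12: 3 x 2 + 6 x 1 = 12 planned; 11/12 = 91.7%.
- Cycles 13-24: 12 x 1 = 12 planned; 11/12 = 91.7%.

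All three exceed 80%. The allowance and the limit agree over the window and conflict only by infusion or by cycle.

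**Step 3: infusions skipped for toxicity.** Take Cycle 2 or 3 with 4 planned infusions.

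| Skipped for toxicity | Skips kept in denominator | Skips removed |
|---|---|---|
| 1 | 3/4 = 75% | 3/3 = 100% |
| 2 | 2/4 = 50% | 2/2 = 100% |
| 3 | 1/4 = 25% | 1/1 = 100% |

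From Cycle 7, removing the only planned infusion gives 0/0, which is undefined, again unless a dose is made up in that cycle.

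**Step 4: completed cycles.** SAP 4.7.1.3 requires compliance for every infusion in the cycle. If toxicity skips are not assessed, the patient in the last row of Step 3 was compliant for the one infusion that counted and completed the cycle. If they are assessed at 0%, the cycle was not completed. The same split arises for a single miss covered by the allowance.

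**The case against.** The strongest reply is that compliance measures adherence, not dose intensity. Protocol 8.12 treats toxicity omissions separately, and Protocol 8.6 itself directs some of them, so not holding them against the patient is reasonable. The parenthesis is attached to the allowance sentence, while the by-cycle ratio is introduced as an additional summary with no stated exclusion. On that reading the patient with three skipped infusions shows 25% and has not completed the cycle. This reading is available and stands as far as it goes, but the text does not choose it.

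A reader might infer that MOR00208 delivery is misreported in both directions. The documents do not support that. After a miss unrelated to toxicity, the lowest class shows the true delivered fraction; the fault there is a contradictory label. Overstated delivery follows only if toxicity skips leave the denominator.

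A reader might also infer that the report hides toxicity. It does not. The SAP summarises the number of infusions (4.7.1.3), temporary interruptions with reasons (4.7.3), and adverse events leading to interruption or any action, split by drug (4.10.1.7.1). It also lists administration records (Listing 16.2.5.1.1).

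Those outputs only partly fill the gap. The infusion count has no scheduled denominator. The interruption table counts patients, not doses lost. Exposure duration (4.7.1.1) runs from the first administration to the last plus an interval, so infusions skipped in between do not shorten it.

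**Conclusion.** The compliance definition for MOR00208 contradicts itself, and this can be shown from the text and the schedule alone. In every cycle, one permitted miss at equal doses gives a ratio of 80% or less, with the Cycle 1 and make-up limits noted in Step 1. The effect of the toxicity exclusion is conditional: 100% instead of 25% in the example, and a completed instead of an uncompleted cycle, if skipped doses leave the denominator. No output is defined so that every omitted infusion is certain to count against the scheduled dose.

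The consequence is confined to the compliance and completed-cycle summaries. The primary endpoint, the incidence and severity of adverse events, does not use the compliance flag, and neither do the FAS and SAF definitions.

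**What to change.** Amend SAP 4.7.4 and 4.7.1.3 as follows.

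1. Report MOR00208 dose given divided by protocol-scheduled dose, by cycle, with every omitted infusion in the denominator and the reason for omission shown. State to which cycle a made-up dose is credited.
2. Define a completed MOR00208 cycle by the infusions actually given, not by the compliance flag.
3. Keep the one-dose allowance and the toxicity exclusion only as an adherence or protocol-deviation rule, applied over Cycles 1-3, 4-12 and 13-24, and separate it from the by-cycle dose summary.

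The cost is SAP wording and a little more programming. Protocol 8.12 has each administered dose recorded in the eCRF, and SAP 4.7.3 already calls for reasons for interruption; that a reason is available for each skipped infusion is an assumption to confirm. The reported delivery figure may look less favourable. No dosing or clinical rule needs to change.

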4.8 Efficacy Analysis

4.8.1 Secondary Endpoint

Single efficacy variable analyzed in this study is: **Best Objective Response Rate (ORR)**

(Best) ORR is defined for Cohort A as percentage of patients achieving a complete response (CR), a partial response (PR) or a partial response with lymphocytosis (PRL) at any time during the study, and for Cohort B as percentage of patients achieving a CR or a PR at any time during the study based on the local assessment. CR, PR or a PRL is defined according to the criteria of the International Workshop on Chronic Lymphocytic Leukemia (IWCLL) for CLL patients (Hallek et al., 2008; see Section 6.3), with the modification that treatment-related lymphocytosis in the absence of other signs or symptoms of disease progression will not be considered as progressive disease (Cheson et al., 2012; Hallek et al., 2012; NCCN NHL 2015 Guidelines). For patients with SLL, assessments will be performed using the Lugano Classification criteria for SLL patients (Cheson et al., 2014). The number of patients and rates will be reported split by cohort.

For derivation of the best ORR, response assessments after a patient has started a new anti-neoplastic therapy will not be taken into account.

Response evaluations (CR, PR, PRL, SD and PD) will be tabulated with counts and percentages for each available visit. Missing response evaluations, or non-evaluable assessments will be taken into account, with patients with missing responses included in the denominator for calculating rates.

The above summary/analysis will be performed using the FAS and PPS.

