9.3.3 Assessment of Efficacy

9.3.3.1 Tumor Response Assessment

Criteria of the International Workshop on Chronic Lymphocytic Leukemia (IWCLL) for CLL subjects (Hallek et al., 2008) will be used to determine rates of response and progression for patients with CLL, with the modification that treatment-related lymphocytosis (Note: PRL is applicable in Cohort A only) in the absence of other signs or symptoms of disease progression will not be considered as progressive disease (Cheson et al., 2012; Hallek et al., 2012; NCCN NHL 2015 Guidelines). For patients with SLL, assessments will be performed using the Lugano Classification criteria for SLL subjects (Cheson et al., 2014).

The secondary endpoint overall response rate (ORR) will be derived from the local review of radiology and clinical data.

Patients who develop a PR will be assessed using MRD testing from peripheral blood as well as from bone marrow, in case PB MRD negativity status was reached. Furthermore, patients who develop a complete response as per standard criteria will be investigated using MRD testing and bone marrow aspiration/biopsy as described in IWCLL (Hallek et al., 2008).

Overall response assessments include physical exams, recording of symptoms, radiographic and hematological evaluations to evaluate for both AEs and for disease progression per the schedule of assessments. If a patient shows signs of progression, the patient may continue on treatment until progression is confirmed by CT scan. The CT scan should be performed and collected with resolution sufficient to allow accurate and consistent comparison of target lesion measurements with subsequent CT scans. The same scan modality should be used for all assessments, and all patients are required to have scans of the neck/chest/abdomen/pelvis.

Baseline tumor assessments must be performed a maximum of 14 days before C1D1. As response is a secondary endpoint of the trial and that PD will be followed by physical examination, CT scans performed prior to screening as part of the regular clinical work-up of the patient will be allowed up to 6 weeks before C1D1. This is to prevent the re-irradiation of patients who have recently undergone a CT scan. However, a CT scan must be performed within the 14 day period prior to C1D1 for those patients with signs of rapidly progressing disease at screening.

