9.3.3.2 Tumor Response Assessment for CLL

Definitions of Tumor Response and Progression

Responses will be categorized locally as CR, PR, PRL, SD, or PD.
(Note: PRL is applicable in Cohort A only.)

The best overall response in the course of the study will be determined. The best overall response is the best response recorded from the start of treatment until disease progression, withdrawal from study or death (taking as a reference for disease progression the smallest measurements recorded since treatment started).

At baseline, up to 6 lymph nodes should be selected as index lesions that will be used to quantitate the status of the disease during study treatment. Ideally, the index lesions should be located in disparate regions of the body. However, it is optimal if mediastinal and retroperitoneal areas of disease are assessed whenever these sites are involved. Any other measurable and abnormal nodal lesions not selected for quantitation as index lesions may be considered non-index lesions. In addition, non-measurable evidence of CLL such as nodal lesions with both diameters < 1.0 cm, extranodal lesions, bone lesions, leptomeningeal disease, ascites, pleural or pericardial effusions, lymphangitis of the skin or lung, abdominal masses that are not confirmed and followed by imaging techniques, cystic lesions, previously irradiated lesions, and lesions with artifacts may be considered as non-index disease. The presence or absence of non-index disease should be recorded at baseline and at the stipulated intervals during treatment. The non-

index disease at baseline will be used as a general reference to further characterize regression or progression of CLL during assessments of the overall tumor response during treatment. Measurements are not required and these lesions should be followed as “present” or “absent”.

A table of response definition by the IWCLL 2008 is provided in [Appendix J](#).

Complete Response

To satisfy criteria for a CR, all of the following criteria must be met:

- No evidence of new disease
- ALC in peripheral blood of $< 4 \times 10^9/L$
- Regression of all index nodal masses to normal size ≤ 1.5 cm in the longest diameter (LDi)
- Normal spleen and liver size
- Regression to normal of all nodal non-index disease and disappearance of all detectable non-nodal, non-index disease

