12 STATISTICAL METHODS AND PLANNED ANALYSES

A Statistical Analysis Plan (SAP) will be prepared after the protocol is approved. This document will provide further details regarding the definition of analysis variables and analysis methodology to address all study objectives. The SAP will serve as a compliment to the protocol and supersedes it in case of differences.

The statistical evaluation will be performed using the Statistical Analysis Software (SAS®) Version 9.3 or higher (SAS Institute, Cary, NC). All data will be listed, and summary tables will be provided. For continuous variables, data will be summarized with the number of subjects (N) (with non-missing values/valid cases), mean, standard deviation, minimum, 25th quartile, median, 75th quartile and maximum, except for pharmacokinetic metrics, where additional statistics may be used. For categorical variables, data will be tabulated with the frequency and percentage of patients/entries for each category.

Missing values will not be imputed. All statistical evaluations will be based on valid cases except for procedures described for calculating response rates or in the case of censoring within the Kaplan-Meier methodology. In the case of incomplete start or stop dates of AEs or concomitant medication appropriate conservative imputation methods will be specified in the SAP.

Baseline values will be defined as the last pre-administration observation used for calculating post-administration changes from baseline.

All data obtained and entered into the database will be provided in separate data listings showing individual patient values. A SAP detailing the statistical analyses and possible deviations from the protocol will be prepared and finalized prior to database lock.

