12.6 Efficacy Analysis

12.6.1 Analysis of Secondary Efficacy Endpoint – ORR

The secondary endpoint is overall response (ORR). ORR is defined for Cohort A as percentage of patients achieving a complete response (CR), a partial response (PR) or a partial response with lymphocytosis (PRL), and for Cohort B as percentage of patients achieving a CR or a PR based on local assessment. CR, PR or a PRL is defined according to the criteria of the IWCLL for CLL subjects (Hallek et al., 2008) for patients with CLL, with the modification that treatment-related lymphocytosis in the absence of other signs or symptoms of disease progression will not be considered as progressive disease (Cheson et al., 2012; Hallek et al., 2012; NCCN NHL 2015 Guidelines). For patients with SLL, assessments will be performed using the Lugano Classification criteria for SLL subjects (Cheson et al., 2014).

Local response evaluations (CR, PR, PRL, SD and PD) will be tabulated with counts and percentages for each available visit. Missing response evaluations will be taken into account, with patients with missing responses included in the denominator for calculating rates. The SAP will specify further sensitivity and supportive analyses, as well as possible evaluation of further response parameters (e.g., best response).

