4.17 Changes in Conduct or Planned Analyses from the Protocol

In the SAP a more detailed information was provided for both the definition of the FAS and the SAF. As per SAP the definition for the SAF was extended in a sense that the SAF is based on the treatment actually received. This extension of the definition is justified as the SAF will be used for all safety-relevant analyses, which have to be interpreted in the context of the treatment that has been actually received. Moreover, for the SAF as per SAP the restriction that at least one post-baseline safety evaluation is required was added.

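### The SAP's response-rate window has no stop at disease progression, while the protocol's best-overall-response window does, and the SAP does not declare the difference

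*SAP*

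**What the plan says.** **SAP 4.8.1.** Best objective response rate is the only efficacy variable in the SAP. For Cohort B it is the percentage of patients "achieving a CR or a PR at any time during the study based on the local assessment"; Cohort A has the same window and adds PRL. One restriction follows: "response assessments after a patient has started a new anti-neoplastic therapy will not be taken into account". Progression is not mentioned as a limit there, and no other SAP section sets one. SAP 4.1.4 adds that unscheduled scans feed the tumor response endpoints.

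**Protocol 9.3.3.2 (CLL).** "The best overall response is the best response recorded from the start of treatment until disease progression, withdrawal from study or death".

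**Protocol 6.2.2 and 12.6.1.** ORR is defined by response category and cohort, with no time window. Section 12.6.1 leaves sensitivity and supportive analyses to the SAP, "as well as possible evaluation of further response parameters (e.g., best response").

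**Protocol 9.3.3.3 (SLL).** The Lugano criteria are tabulated, with no window for best response.

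**Precedence and disclosure.** Protocol section 12: "The SAP will serve as a compliment to the protocol and supersedes it in case of differences". SAP 4.17, which records changes from the protocol, deals only with two analysis sets: "In the SAP a more detailed information was provided for both the definition of the FAS and the SAF".

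**The concern.** The two documents give different end points for the same quantity, and the one with the later end point governs. A programmer who follows SAP 4.8.1 literally takes the best assessment before new therapy, including any made after progression. A reader who knows Protocol 9.3.3.2 would assume that those assessments had been dropped.

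The stake is the meaning of the study's one efficacy figure. It is assessed locally, in an open-label, non-randomized study with about 12 patients per cohort, so a single reclassified patient visibly moves the rate. Because SAP 4.17 is silent, a reader of the report would not learn that the window had been widened.

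**Working it through.** The plan has no figure of its own to reproduce: SAP 3.10 states that no formal sample size calculation was made and no hypothesis test is planned. The check is a comparison of texts, followed by the size of one reclassification.

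**Step 1. The two windows.**

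| | SAP 4.8.1 | Protocol 9.3.3.2 |
|---|---|---|
| Opens | not stated; during the study | start of treatment |
| Closes at progression | no | yes |
| Closes at withdrawal or death | implied by the end of participation | yes |
| Closes at new anti-neoplastic therapy | yes | not stated |
| Disease | CLL and SLL | CLL section only |

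The windows differ for any response dated after progression and before new therapy.

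**Step 2. Which assessments can fall in that gap.**

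- *Suspected progression, never confirmed.* Protocol 9.3.3.1 says: "If a patient shows signs of progression, the patient may continue on treatment until progression is confirmed by CT scan". Section 9.3.3.2 keeps the patient on study treatment, under observation, while true progression is uncertain. A later PR in such a patient is not a response after progression under the protocol. Both documents count it, so there is no discrepancy.
- *Progression confirmed as persistent and dated back.* Section 9.3.3.2 sets the date at the first objective documentation. A response recorded between that date and confirmation counts under the SAP but not under the protocol. Such a reading fits poorly with persistent progression, so it should be uncommon.
- *Definitive progression, then an end-of-treatment or unscheduled assessment.* Protocol 9.2.9 includes a response assessment at the end-of-treatment visit, although 9.3.3.1 requires the scan only if none was done within 28 days. A response recorded there before new therapy counts under the SAP only.
- *30-day safety follow-up.* No CT or MRI is scheduled (Protocol Table 10, SAP Table 2), so this visit adds little.
- *After new anti-neoplastic therapy.* Excluded by SAP 4.8.1.

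The second and third cases are the exposure.

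**Step 3. Direction.** Best response is the best value in a set of assessments. Enlarging the set cannot make it worse, and the denominator (the FAS) does not change. The effect on ORR is therefore zero or positive.

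**Step 4. Size.** Cohort size is 10 to about 12 (SAP 3.2, 3.10). Change in ORR = affected patients / n.

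- One patient: 1/12 = 8.3 points; 1/10 = 10.0 points.
- Two patients: 2/12 = 16.7 points; 2/10 = 20.0 points.

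For scale, with assumed counts and exact (Clopper–Pearson) 95% intervals: 6/12 = 50.0% (21.1 to 78.9) becomes 7/12 = 58.3% (27.7 to 84.8). One such patient moves the estimate by far less than the sampling uncertainty at this size.

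**The case against.** The strongest reply is that participation nearly ends at progression anyway. Progressive disease requires study medication to stop (Protocol 7.1, SAP 3.2). Permanent discontinuation is one of the events that end the main study for the individual (Protocol 7.4). SAP 3.4 places the end-of-treatment visit at documented progression. This stands, and it is why the exposure is small. It does not close the gap, because the end-of-treatment visit carries a response assessment, unscheduled scans count, and the progression date can be moved back.

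A second reply is that the protocol's ORR definitions contain no progression limit and that 12.6.1 leaves best response to the SAP. This stands in part. The SAP does not contradict the wording of the ORR endpoint itself; it departs from the best-overall-response window in the CLL section. But permission to specify further response parameters does not cancel a window that the protocol states elsewhere, and a deliberate change belongs in SAP 4.17.

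A third reply is that the effect would be visible. Responses are tabulated by visit (SAP 4.8.1), tumor assessments are listed (Listings 16.2.6.1 and 16.2.6.2), and the swimmer plot in SAP 4.3 marks when best response is reached. That helps a careful reader but does not correct the headline rate.

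A reader might also infer that treating through unconfirmed progression generates the problem: a PD later read as PR on the same drugs would be counted wrongly. The documents do not support this. They treat such a patient as not having definitively progressed, so the PR is legitimate under both.

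**Conclusion.** The discrepancy is real and undeclared. SAP 4.8.1 has no stop at progression, Protocol 9.3.3.2 has one, the SAP "supersedes it in case of differences", and SAP 4.17 does not mention the change.

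Its practical reach is limited. Each affected patient adds 8.3 points at n = 12 or 10.0 at n = 10, upward only, but the documents give no basis for expecting any particular number of such patients, and it may be none. ORR is secondary and descriptive, so no error rate is involved.

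The conclusion assumes that SAP 4.8.1 would be programmed as written and that suspected progression which is never confirmed is not progression. It does not extend to a claim that ORR will be inflated. For SLL, the protocol sets no window for the SAP to depart from, so there the point is a gap to fill.

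**What to change.** Add one sentence to SAP 4.8.1, covering both CLL and SLL: best response is derived from assessments up to definitive disease progression or the start of new anti-neoplastic therapy, whichever is earlier. Progression is dated as in Protocol 9.3.3.2, that is, at its first objective documentation once it has been confirmed as persistent. State also that a suspected progression which is never confirmed does not close the window. A cut at the first recorded PD regardless of confirmation would be wrong: it could discard responses that the protocol allows and bias ORR downward.

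If the wider window is intended, list it in SAP 4.17 with the reason.

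The cost is one clause and a small change to the derivation. No new data are needed, because PD is already recorded and tabulated by visit.
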